5.4.3. Licensed QIV

The licensed QIV will be purchased by the Sponsor through a distributor for provision to the sites

The licensed vaccines will contain HA proteins from each of the 4 monovalent strains, i.e., two influenza A subtype viruses and two influenza type B viruses recommended for use in the 2021-2022 influenza season. The proteins are suspended in a sodium phosphate buffered isotonic sodium chloride solution and may contain trace amounts of egg protein, formaldehyde and Triton X-100. The vaccines are clear and slightly opalescent in color. They will be supplied in vials or pre-filled syringes, neither of which contain natural rubber latex. The pharmacist will shake the vial or syringe before administering the dose as an intramuscular injection.

5.5. Storage and Drug Accountability

The Investigator (or designee) is responsible for the safe storage of all study treatments assigned to the clinical site, in a locked, secure storage facility with access limited to those individuals authorized to dispense the study drugs and maintained within the appropriate ranges of temperature. All study drugs must be stored as specified at delivery and in the original packaging. Instructions for the storage and handling of the study drugs will also be provided to the clinical site

5.5.1. Study Vaccine

The M2SR vaccine will be delivered frozen and must be stored frozen at < -65°C in the provided multi-vial boxes. Each vaccine vial is a single-use vial. Once the vial contents have been thawed, the vial must be stored at 2-8°C prior to use in vaccine administration. The thawed vial contents will remain stable in the Sponsor-identified cryovials, for up to 8 hours. Any vaccine product that has been thawed and held at 2-8°C for longer than 8 hours is no longer suitable for use in the study and must be accounted for. Such product will be labeled as damaged and will be quarantined at room temperature until the study monitor conducts on-site drug accountability. After that, this product should be destroyed per clinic Standard Operating Procedures (SOPs) and a certificate of destruction, or equivalent should be filed on site and provided to the Sponsor for internal filing.

Investigational product must be stored under temperature-controlled and monitored conditions. The site will also maintain a temperature log record of the relevant equipment for IP storage. Should an excursion in storage conditions occur, the clinical site must not further dispense the affected study vaccine until after notification and consultation with the Sponsor.

The Investigator is responsible throughout the study for ensuring inventory and account record of all study drugs received at the clinical site. All drug accountability records must be stored in the site file and must be readily available for inspection by the study monitor and/or auditor, and open to regulatory inspections at any time.

As misallocations of study drug may have a detrimental effect on subjects' safety and/or the study drug's efficacy and are a potential source of bias, utmost care should be taken to correctly dispense the study drugs as assigned by the randomization code.

The vaccine and placebo should be dispensed under the supervision of the Investigator, a qualified member of the clinical staff, or by a hospital/clinic pharmacist or designee. The pharmacist or designee must maintain accurate records demonstrating date and amount of vaccine and the placebo supplied to whom and by who. The investigational vaccine and placebo will be supplied only to subjects participating in the study.

The Sponsor's designated study monitor will periodically check the supplies of vaccine and the placebo held by the Investigator or pharmacist/designee to ensure accountability and appropriate storage conditions of all vaccine and placebo used.

Unused vaccine and placebo must be available for verification by the study monitor during onsite monitoring visits. Any discrepancies between returned and expected returned vaccine and placebo should be explained and documented.

After the database has been locked and all on-site drug accountability has been completed by the monitor, any unused vaccine (including neat and diluted remnants) may be returned to the Sponsor or destroyed at the clinical site with the Sponsor's written permission (in this case a certificate of destruction or equivalent will be provided and filed in the electronic Trial Master File [eTMF]).

Hazardous materials such as used ampoules, needles, syringes and vials containing hazardous liquids, should be disposed of immediately in a safe manner and therefore will not be retained for drug accountability purposes.

5.5.2. Placebo

Each placebo cartridge is a single-use container. The solution will be stored at USP controlled room temperature $(20-25^{\circ}\text{C})$ prior to use in treatment administration. The contents may be used up to the date of expiry as stated by the manufacturer.

Procedures for handling and storage of the commercially available placebo are detailed on the product-specific labels.

5.5.3. Licensed QIV

The licensed QIV is supplied as vials or prefilled syringes without needles. The QIV will be stored refrigerated at 2-8°C. Do not freeze this vaccine. If product is frozen it must be discarded. The contents may be used up to the date of expiry as stated by the manufacturer.

5.6. Blinding

The blind will be maintained during this trial, including use of the following measures:

- 1. All subjects, whether receiving Sing2016 M2SR vaccine or placebo, will undergo the same procedures, i.e., administration, AE assessment, blood collections, nasal swabs, etc.
- 2. The unblinded pharmacist or designee will prepare doses (active and placebo), fill delivery devices and apply an opaque label to the device barrel to obscure any coloration of the contents.
- 3. The unblinded site staff and unblinded study monitor will agree to maintain the blind by not providing details of the dose (active or placebo) to any blinded clinic staff including the Investigator and to study subjects. Furthermore, the unblinded individuals will be restricted from participating in other study procedures the interpretation of which could be impacted by their unblinded status, such as evaluation of AEs.
- 4. If any blinded investigational site staff learn of treatment assignments, a record of the event will be maintained, and the Investigator will be informed. The Investigator will consult with FluGen on how to preserve the blind.
- 5. Labs supplied with subject samples for analyses will be blinded to treatment assignment.

Except for the unblinded statistician or computer programmer who generates the randomization list, the unblinded pharmacist(s) or their designee(s) who prepare the study product for administration and the unblinded study monitor who may observe the study product preparation and performs IP accountability, all subjects, the Investigator, statistical programmers and all

clinical site staff will be blinded to IP treatment (vaccine or placebo). All clinic staff who may be involved in making assessments of safety (including local reactions) will be blinded to treatment. Should a blinded monitor observe study product preparation, precautions must be taken to maintain the blind.

Masking of the IP (vaccine or placebo) will be described in the Pharmacy Manual.

The randomization schedule will be inaccessible to the Investigator or to the blinded study team (monitors and/or FluGen team) during the study. After the final study visit is complete for all subjects, after database lock, and after reconciliation with pharmacy and site records, the randomization code will be provided to the Study Statistician to enable data analysis by the Sponsor.

The unblinded Statistician will provide the randomization list to the unblinded pharmacist or their designee. This list will be used to prepare study product dosages and in the event of an emergency code break (see below).

In the event of a medical emergency wherein knowledge of the IP treatment assignment will influence the subject's care, the PI may be provided with the IP treatment assignment for that subject, at the discretion of the PI. The unblinded pharmacist or their designee will use the IP treatment assignment code to break the blind for the PI only in case of emergency. The PI will contact the FluGen Medical Monitor and document the event with the information regarding the reasons for unblinding as soon as possible, and no later than 24 hours after such unblinding. In the event the IP treatment code is broken, it will be broken ONLY for the subject in question. The reason for unblinding will be documented in the subject's paper source. Subjects who are unblinded for any reason during their participation in the study will not be replaced and will be withdrawn immediately from the study; however, all attempts will be made to collect safety data through 28 days post-dose of the vaccine/placebo. In the event of a request to break a treatment code, the study monitor will be notified within 24 hours and the rationale for breaking the code will be documented.

5.7. Dose and Administration

5.7.1. Investigational Vaccine

A rationale for the dose of Sing2016 M2SR vaccine selected in this study is provided in Section 3.6.2.

Subjects will be randomly and sequentially assigned, according to the randomization schedule and in a blinded fashion, to vaccine or placebo in a 2:1 ratio.

Each vaccine and placebo dose will be filled into two sterile 1 mL polypropylene syringes (HenkeJect) that are each fitted with a Teleflex MAD300 sprayer for intranasal delivery (Figure 2) by the unblinded pharmacist or designee.

Figure 2: Image of the MAD300 Sprayer Device Fitted to a Syringe

To fill the syringe, the contents are drawn into the syringe barrel via an 18-gauge needle. The needle is removed and replaced with the MAD300 sprayer via a Luer lock fitting. A sterile cap is fitted to the end of the sprayer to generate a closed system until time of dose administration. Further details for filling and actuating the spray device are provided in the Pharmacy Manual. Components for IP dosing will be supplied by the Sponsor. The pharmacist or designee will wrap an opaque label completely around the circumference of the syringe barrel to conceal any color of the liquid contents and will use an indelible marker to record the subject's identification (ID) on the label. The clinical staff credentialed to administer vaccines will then use the masked, filled spray device to administer the dose (active or placebo) intranasally to the subject.

For delivery, subjects will receive a single intranasal dose of vaccine (or placebo) via two MAD300 spray devices. Subjects will be in a semi-recumbent position and receive ~50% dose volume per nasal cavity by employing 2 spray devices. Subjects will remain semi-recumbent and under observation for approximately 30 minutes and will not be allowed to blow their noses, eat, or drink during this time; any deviations are captured in the source documents and reported to the study monitor/clinical project manager.

Any deviation from the dose defined in the protocol must be documented on source and in the electronic case report form (eCRF) system.

5.7.2. Licensed Influenza Vaccine

See package inserts for instruction on how to prepare and administer the licensed vaccine. At time of QIV administration, subjects who are younger than 65 years of age will receive a standard QIV and those who are at least 65 years of age will receive a QIV indicated for people over 65 years of age. The vaccines will be prepared and administered by the pharmacist or designee per instructions in the package insert.

5.8. Treatment Compliance

Monitoring treatment compliance is not applicable because treatment will be administered per protocol in the clinic by study personnel.

5.9. Prior and Concomitant Therapy

The use of concomitant therapies should be kept to a minimum throughout the study. All therapies administered (prescriptions and over-the-counter medications), other than the vaccine, from informed consent until the final study visit, must be recorded in the source documents and in the concomitant therapy section of the eCRF (name of the drug, dosage, route and dates of administration).

In the event that medical conditions after study treatment dictate use of medications, subjects are encouraged to obtain adequate care, comply with the course of therapy as prescribed by their physician, and inform the Investigator as soon as practical.

Subjects may receive a vaccine that is licensed or under an EUA if it is the opinion of the investigator that such treatment is appropriate and necessary. The preference, when possible, is to avoid such treatment during the 28 days post-visit 01.

The Sponsor must be notified in advance (or as soon as possible thereafter) of any instances in which prohibited therapies are administered to a study subject.

Female subjects of childbearing potential and non-vasectomized male subjects having a female partner of childbearing potential must agree to the use of an effective method of contraception throughout the study, as outlined in Section 4.1. The use of oral, injectable, and implantable hormonal contraceptives is to be recorded in the source documents and in the concomitant therapy section of the eCRF.

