4. **Prior and Concomitant Therapy**: (Section 5.9 Prior and Concomitant Therapy) Subjects may receive a vaccine that is licensed or under an EUA if it is the opinion of the investigator that such treatment is appropriate and necessary. The preference, when possible, is to avoid such treatment during the 28 days post-visit 01.

Rationale: Added language to provide clarification regarding vaccine administration during the study participation.

5. Schedule of Events: (Section revised : Section 6.1.1 Table 2: - Schedule of Events – IP Administration)

Updated Schedule of events

Rationale: Update to the schedule of events table to remove V01 hematology and chemistry (Footnote remains to provide additional clarification). Removal of vial weights.

6. Screening Period: (Section revised: Section 6.1.2 Screening Period)

Subjects will be re-confirmed for eligibility on Day 1 (V01) prior to dose administration. Chemistry and hematology at V00 will serve as eligibility and baseline values unless collected more than 28 days prior to V01. In such case the lab tests will be redone to establish baseline only.

Rationale: Added language to provide clarification regarding safety lab collection.

7. **Urine Samples**: (Section revised: Section 6.2.1.6 Urine Samples)

Results are obtained by comparing the color block on the canister to those on the reagent strips where the color blocks enclosed by the black box are considered Normal. If dipstick urinalysis is Abnormal/positive for protein, blood, nitrite and/or leukocyte esterase, a microscopic examination for white blood cells (WBC), red blood cells (RBC), bacteria, casts, and epithelial cells will be performed. Crystals, casts, and bacteria will only be reported if present.

Rationale: Added language to provide clarification regarding urine sample collection.

8. **Bioanalysis**: (Section revised: Section 6.2.2 Bioanalysis)

Blood samples for determination of the concentration of analytes specified in Appendix 3 will be analyzed by a qualified vendor under the responsibility of the Sponsor, using validated analytical methods.

Rationale: Language previously stated "Blood and urine samples..." however urinalysis is being performed by use of dipstick.

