- 8. Recent (within 14 days) known exposure to Covid-19 through a close contact as defined by CDC and/or confirmed Covid-19 infection within the past 3 months.
- 9. Experienced a life-threatening reaction(s) after a previous administration of any vaccine or experienced an allergic reaction after a previous administration of any influenza vaccine or component. In addition, a history of allergy/hypersensitivity to any vaccine (M2SR or licensed QIV) component (sucrose, sodium chloride, phosphate, glutamate, egg protein, formaldehyde, octylphenol ethoxylate [Triton®X-100]), or material in either the nasal or intramuscular delivery device (polycarbonate, polypropylene, synthetic rubber).

- 10. Females who are pregnant or nursing.
- 11. Non-vasectomized males with female partners of childbearing potential who are unwilling to use a highly effective form of contraception from the time of enrollment through at least 28 after administration of the investigational product. Males also may not donate sperm through at least 90 days after receiving the investigational product.
- 12. Blood disorder (easy bruising or bleeding) that may prolong bleeding and for which Investigator deems it would be ill-advised to administer an intramuscular vaccine.
- 13. History of receipt of any live virus vaccine within 56 days of study entry, licensed or investigational vaccine within 28 days of Visit 01 or investigational drug within the past six months. An exception is made for receipt of a Covid-19 vaccine whether licensed or under emergency use authorization (EUA) as long as the final dose was given at least 28 days prior to Visit 01.
- 14. Planned receipt of licensed vaccine, other than the study-provided licensed influenza vaccine, during the 28 days following Visit 01 or another investigational vaccine or investigational drug during the study period.
- 15. Receipt of blood/plasma products or immunoglobulin within 6 months before administration of the investigational product or planned for during the period of study participation.
- 16. Donation of blood or blood product of at least approximately 1 pint (~470mL) within 60 days of IP receipt or planned within 3 months (84 days) after IP administration.

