5.9.2. Prohibited Concomitant Therapies

The following medications are not permitted in the study:

- Concomitant use of any new (not previously used by subject or dosage changed within past month) prescription (except for contraceptive pills, implants, transdermal or injections), new vitamins or new dietary supplements. Over-the-counter (OTC) medications are discouraged but allowed for 7 days prior to IP vaccination and continuing until 7 days after last vaccination. Any such use of OTC must be recorded in the source documents along with the associated AE (if applicable).
- Any licensed vaccine, other than the study-provided licensed influenza vaccine, during the 28 days following Visit 01 or another investigational vaccine or investigational drug during the study period.
- Receipt of blood/plasma products or immunoglobulin during the study period.

Any medication that is not covered by the permitted and non-permitted medication sections can be allowed at the discretion of the Investigator and documented on eCRF.

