7.4. Removal of Subjects from the Study

Subjects have the right to withdraw from the study at any time for any reason, including personal reasons. A subject can withdraw without giving a reason. The Investigator should however try to determine why a subject withdraws from the study and document the reason for withdrawal in the source documents and in the EDC system.

Subjects may be withdrawn from the study in the event of:

- Meeting any of the halting rules in Section 7.3
- A severe AE or SAE;
- Difficulties in obtaining blood or other samples;
- Failure of the subject to comply with the protocol requirements or to cooperate with the Investigator.

Subjects must be withdrawn from the study in the event of:

- Withdrawal of consent
- Lost to follow-up
- Death
- Termination of the study by the Sponsor (described in Section 7.2)
- For safety reasons, it being in the best interest of the subject that he/she be withdrawn, in the Investigator's opinion;
- A positive pregnancy test (the subject or, if reported by a male subject, his female partner), or if the subject/partner is non-compliant with the contraception requirements (see Section 4.1);
- Lab confirmed infection with SARS-CoV-2
- Development of a medical condition that requires concomitant treatment with a prohibited therapy (see Section 5.9.2);
- Breaking of the randomization code during administration of the study drug. If the code is broken for safety reporting purposes, the subject may remain in the study; however, in such cases subject and site staff will remain blinded to IP treatment.

The monitor and Sponsor will be informed in the event of a subject being withdrawn from the study. In case of withdrawal due to an SAE (for details on AE reporting see Section 9.5), the Sponsor should be notified within 24 hours; in case of withdrawal for other reasons; the Sponsor should be notified within 2 days from the event.

Subjects who are withdrawn from the study prior to completion of the scheduled study procedures for any reason (AE, withdrawal of consent, etc.) should be contacted by phone for a safety follow-up 4 weeks after vaccination. In case of an AE, the appropriate follow-up will be done.

Subjects who are withdrawn from the study will not be replaced.

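### Protocol 5.9 allows, on investigator judgement, a licensed vaccine that 5.9.2 forbids in the 28 days after Visit 01, so notification, deviation and withdrawal status conflict for an unplanned dose

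*Protocol*

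**What the plan says.** **Permission.** Protocol 5.9: "Subjects may receive a vaccine that is licensed or under an EUA", subject to the investigator's opinion that it is appropriate and necessary. Avoiding the 28 days after Visit 01 is a preference, to be followed when possible. The change list at the front of v3.0 gives the reason for this text: "Added language to provide clarification regarding vaccine administration during the study participation".

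**Prohibition.** Protocol 5.9.2 includes among medications that are not permitted: "Any licensed vaccine, other than the study-provided licensed influenza vaccine, during the 28 days following Visit 01". It closes with a discretion clause: "Any medication that is not covered by the permitted and non-permitted medication sections can be allowed at the discretion of the Investigator".

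**Rules that depend on the answer.**
- Notification, Protocol 5.9: "The Sponsor must be notified in advance (or as soon as possible thereafter) of any instances in which prohibited therapies are administered".
- Deviations, SAP 7: prohibited therapies are not flagged in the medication tables or listings but appear under protocol deviations.
- Withdrawal, Protocol 7.4: mandatory if a medical condition develops that needs a therapy prohibited by 5.9.2.
- Evaluable sets, SAP 2.1.1.4 and 2.1.1.5: subjects with major deviations thought likely to interfere with the immunogenicity evaluation are left out. SAP 4 has staff agree on major deviations before lock and cites a Deviation Handling Plan, Version 1.0 of 27 July 2021.

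**Entry rule.** Exclusion criterion 14 already bars "Planned receipt of licensed vaccine, other than the study-provided licensed influenza vaccine, during the 28 days following Visit 01".

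**Version.** SAP 1.1.1 names protocol v2.0 of 10 May 2021 as its basis. The protocol supplied is v3.0 of 9 September 2021.

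**The concern.** Sections 5.9 and 5.9.2 cover the same products over the same 28 days. Neither refers to the other or says which prevails. A site that follows 5.9 has given an allowed vaccine and has nothing to notify or list. A site that follows 5.9.2 has given a prohibited one and must do both. If the vaccine is needed for a condition that arose after entry, 5.9.2 read with 7.4 requires withdrawal of a subject for a dose that 5.9 allows.

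On the analysis side, a dose ruled a major and interfering deviation removes the subject from the IP evaluable set (IPEVAL). SAP 9.2.1 also uses that set for the 7-day diary summaries, which serve the first primary endpoint in Protocol 2.2.1. A decision about interference with antibody results would then remove solicited-reaction data from a primary safety table.

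**Working it through.** The plan gives no figure on this point, so the check is a comparison of texts and some date arithmetic.

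**1. Does another clause settle the conflict?** The discretion clause in 5.9.2 reaches only medications that neither list covers. A licensed vaccine inside 28 days is named in 5.9.2, so the clause does not apply. SAP 1 gives the SAP precedence where it disagrees with the protocol, but the SAP does not say whether such a vaccine is prohibited.

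**2. Which doses are affected?** Criterion 14 removes doses planned at entry. Section 5.9.2 does not name products available only under emergency authorisation. What remains is a licensed non-study vaccine whose need arises after entry.

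**3. Consequences for one such dose.**

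| Question | Following 5.9 | Following 5.9.2 |
|---|---|---|
| Allowed? | Yes, on investigator judgement | No |
| Sponsor notification (5.9) | Not triggered | Required |
| Deviation listing (SAP 7) | None | Listed |
| Withdrawal (7.4), only if a medical condition requires the dose | Not triggered | Mandatory |
| IPEVAL (SAP 2.1.1.4) | No deviation, so no exclusion on this ground | Lost only if ruled major and interfering |

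**4. Document dates relative to v3.0 (9 September 2021).**
- Protocol v2.0, 10 May 2021: 21 + 30 + 31 + 31 + 9 = 122 days earlier.
- Deviation Handling Plan, 27 July 2021: 4 + 31 + 9 = 44 days earlier.
- SAP, 3 June 2022: 21 + 31 + 30 + 31 + 31 + 28 + 31 + 30 + 31 + 3 = 267 days later.

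**5. Who could meet the conflict?** 9 September minus 28 days is 12 August 2021. A subject dosed by 12 August reached the end of the window no later than the date of v3.0. A subject dosed between then and 9 September met v3.0 for part of the window. QIV had to be finished by early November and at least 28 days after IP, so the last IP doses fall around early October. Only subjects dosed from 9 September to about early October could have the whole window under v3.0. Protocol 11.1 requires IRB approval before an amendment takes effect, which may shorten this further. The documents do not give the number of subjects in each period.

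**6. Timing against the sample.** The 5.9.2 window ends on Day 1 + 28 = Day 29. The V03 sample may be taken on Day 29 ± 3, that is, Days 26 to 32. A dose can therefore fall inside the prohibited window yet after the sample, where it cannot affect the IP antibody result. This favours a judgement on each case over automatic exclusion.

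**7. Who decides?** SAP 4 puts statistical staff in the deviation meeting. SAP 1.1.2.3 gives the consulting statistician and programmers the treatment codes throughout the trial. Nothing in SAP 4 says that the decision is made blind.

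**The case against.** The strongest reply is that the two sections can be read together: the vaccine is prohibited by default, allowed when necessary, and notified to the Sponsor, because the notification paragraph directly follows the permission in 5.9. That is probably what was meant, and a careful site might act on it. The text does not say it, however, and this reading still leaves deviation listing and the 7.4 trigger open.

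Other parts of the reply stand and limit the point:
- A reader might infer from the v2.0 citation that the analysis plan was written before the permission existed. It was not. The SAP is later than v3.0, describes sampling from the end of September 2021, and in 8.7 allows an exploratory look at subjects given Covid vaccine during the study. The citation is out of date, but that does not show the authors were unaware of such doses.
- A reader might infer that no evaluable-set rule applies. A general one does, applied centrally before lock, which also limits site-to-site differences in set membership. Only a vaccine-specific rule is absent.
- The Deviation Handling Plan predates v3.0, but its content is not available and it may already classify non-study vaccines. Its date alone does not show it to be inadequate.
- A reader might count all 120 planned subjects for 28 days each as exposed to the conflict. The dates in the working rule that out.
- Adverse event summaries use the IP safety set (SAP 9), so IPEVAL membership does not affect them.

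**Conclusion.** The conflict is real and stands in the current text. It concerns an unplanned licensed non-study vaccine in the 28 days after Visit 01 while v3.0 is in force. For that dose the protocol gives opposite answers on Sponsor notification and deviation listing and, when a medical condition requires the dose, on mandatory withdrawal.

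The effect on results cannot be estimated, because the documents do not say how many such doses were given. It is likely small. The dose must be licensed, unplanned and inside the window, and it changes the analysis sets only if ruled both major and interfering, or if withdrawal costs the subject the required visit. The trial has no powered comparison or formal hypothesis test. The documents do not support reading this as a general failure of the evaluable sets, or as automatic loss of every vaccinated subject. The case for a change rests on contradictory instructions to sites, a possible needless withdrawal, and possible loss of diary data from a primary safety table.

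**What to change.** 1. **Protocol 5.9.2, vaccine bullet.** Add: *except a non-influenza vaccine the investigator judges appropriate and necessary under 5.9; the Sponsor must still be notified and the dose and date recorded.* The notification words are needed because an excepted dose would otherwise no longer count as prohibited and the duty in 5.9 would lapse. Keep a non-study influenza vaccine in the 28 days prohibited, and say so in 5.9. Criterion 14 stays as it is.
2. **Protocol 7.4.** State that an excepted dose is not by itself a reason for withdrawal.
3. **SAP 1.1.1, 2.1.1.4, 2.1.1.5 and 4.** Cite protocol v3.0. Leave exclusion from IPEVAL and QIVEVAL for a non-study vaccine to the existing interference test, and state that the decision is made by people blind to treatment, taking account of whether the dose came before the sample.
4. **SAP 9.2.1.** Keep the 7-day diary data of any subject excluded from IPEVAL because of a non-study vaccine.

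The cost is a few wording changes and no new data, since 5.9 already requires therapy names and dates in the eCRF. If a further protocol amendment is not practical, items 3 and 4 still settle the analysis side. The downside is that subjects given a permitted vaccine may stay in the immunogenicity sets, with whatever effect that vaccine had.
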